7.4. Dosage Modification

See Section 7.2.1.

7.5. Preparation/Handling/Storage/Accountability

The investigator or his/her designee is responsible for confirming appropriate temperature conditions have been maintained during transit for all study treatment received and any discrepancies are reported and resolved before use of the study treatment.

Only participants enrolled in the study may receive IP and only authorized site staff may supply or administer study treatment. All study treatments should be stored in an environmentally controlled and monitored (manual or automated) area in accordance with the labeled storage conditions with access limited to the investigator and authorized site staff.

All insulin products must be stored at the investigative site under refrigerated conditions (between 2°C and 8°C) in a locked and secure place. Insulin must not be frozen.

In-use insulins should be maintained at room temperature, and refrigerated material should be warmed to near room temperature before injection. In-use insulin must not be used after 28 days.

The investigator is responsible for study treatment accountability, reconciliation, and record maintenance (such as receipt, reconciliation, and final disposition records).

7.6. Treatment Compliance

The investigator or designee will assess compliance of the patient at each visit, based on a review of the patient's glycemic control, adherence to the visit and treatment schedule, and completion of patient eCOA. Patients who are deemed noncompliant will receive additional diabetes education and training, as required, and the importance of compliance with the protocol will be reinforced. Patients who, in the opinion of the investigator, are deemed consistently noncompliant may be discontinued from IP or from the study. No specific study data will be collected for analysis of treatment compliance.

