7.3. Blinding

This is a double-blind study. The treatment groups, LY900014 and insulin lispro, will be administered immediately (0-2 minutes) prior to each meal in a double-blind manner. Investigators, patients, and study site personnel will be blinded to assigned dosing regimens throughout the study.

To preserve the blinding of the study, the Lilly study team will remain blinded throughout the study; only a minimum number of Lilly personnel will see the randomization table and treatment assignments before the study is complete.

Emergency unblinding for AEs may be performed through the IWRS, which may supplement or take the place of emergency codes generated by a computer drug-labeling system. This option may be used **ONLY** if the patient's well-being requires knowledge of the patient's treatment assignment. Unblinding events are recorded and reported by the IWRS.

If an investigator, site personnel performing assessments, or patient is unblinded, the patient must be discontinued from IP and should remain in the study.

In case of an emergency, the investigator has the sole responsibility for determining if unblinding of a patient's treatment assignment is warranted. Patient safety must always be the first consideration in making such a determination. If the investigator decides that unblinding is warranted, the investigator should make every effort to contact the Lilly clinical research physician (CRP/CRS) prior to unblinding a patient's treatment assignment unless this could delay emergency treatment of the patient. If a patient's treatment assignment is unblinded, Lilly must be notified immediately.

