8.1. Discontinuation from Study Treatment

In the event that the patient is discontinued from the study treatment, the investigator should encourage the patient to remain in the study for continued safety monitoring.

Lilly recognizes the importance of complete data collection. This study includes elements to minimize missing data. Randomized patients who are discontinued from IP before study completion are encouraged to remain in the study for continued monitoring. For patients who remain in the study after early discontinuation of IP, both efficacy (including HbA1c) and safety data will be collected at scheduled visits. The difference between stopping IP and discontinuing the study will be explained to patients as part of the informed consent, and patients will be encouraged to continue in the study even if they stop study drug. In addition, study site investigators will be trained on the importance of complete data collection, with additional re-education of sites and patients as necessary.

8.1.1. *Permanent Discontinuation from Study Treatment*

Patients will be discontinued from the IP in the following circumstances:

- The investigator may decide that the patient should stop IP. If this decision is made because of an AE, SAE, or a clinically significant laboratory value, the study drug is discontinued for that patient and appropriate measures are to be taken. Lilly or its designee is to be alerted.
- The patient may decide to stop IP.
- If the patient becomes pregnant.
- If an investigator, study site personnel performing assessments, or patient is unblinded, the patient must discontinue IP.
- If the patient, for any reason, requires treatment with another therapeutic regimen or therapeutic agent that has been demonstrated to be effective for treatment of the study indication. Discontinuation from IP should occur prior to introduction of the new agent.
- Use of prohibited concomitant medication, see [Table ITRN.8](#).
- If the patient has not taken IP for more than 14 consecutive days.

Discontinuation of the IP for abnormal liver tests **should be considered** by the investigator when a patient meets one of the following conditions after consultation with the Lilly designated medical monitor:

- ALT or AST >8X ULN.
- ALT or AST >5X ULN for more than 2 weeks.
- ALT or AST >3X ULN and TBL >2X ULN or prothrombin time >1.5X ULN.

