8.1.3. Discontinuation of Inadvertently Enrolled Patients

If the sponsor or investigator identifies a patient who did not meet enrollment criteria and was inadvertently enrolled, a discussion must occur between the Lilly CRP and the investigator to determine if the patient may continue in the study. If both agree it is medically appropriate to continue, the investigator must obtain documented approval from the Lilly CRP to allow the inadvertently enrolled patient to continue in the study with or without treatment with IP.

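### Protocol 7.6 and 8.2 let a site end study follow-up of a randomized patient for noncompliance, creating avoidable and possibly outcome-related missing Week 26 data for the ITT estimand

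*Protocol*

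**What the plan says.** Protocol 7.6 states that patients who, in the investigator's judgement, "are deemed consistently noncompliant may be discontinued from IP or from the study". The per-visit compliance assessment behind that decision is "based on a review of the patient's glycemic control, adherence to the visit and treatment schedule, and completion of patient eCOA". The first response to poor compliance is more education and training. The section also states: "No specific study data will be collected for analysis of treatment compliance".

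Other sections bear on whether such a patient stays in follow-up:

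- **Protocol 8.1** states an aim of minimizing missing data and provides for HbA1c collection after IP stops. It adds: "Randomized patients who are discontinued from IP before study completion are encouraged to remain in the study for continued monitoring".
- **Protocol 8.2** lists the investigator's decision, without further criterion, as a possible reason for discontinuing from the study.
- **Protocol 7.3** uses a firmer form for unblinding: "the patient must be discontinued from IP and should remain in the study".
- **Protocol 5.3.1** has patients who stop IP but stay in the study complete all remaining visits. Those who leave the study have an early discontinuation visit and then Visit 801.
- **Protocol 10.3.3.1 and SAP 6.11.1** define the ITT analysis on all data through Week 26 regardless of IP use. Missing values are imputed from same-arm patients who stopped IP and completed the study without missing data. SAP 6.11.1 adds a return-to-baseline fallback.

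**The concern.** The ITT estimand needs the Week 26 value of patients who have stopped IP, and the visit schedule is built to collect it. Section 7.6 nevertheless offers the site a second exit, from the study itself, even for a patient who is willing to keep attending. Once that exit is used, the Week 26 HbA1c and mixed-meal test are not collected.

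Three consequences follow. First, the missingness can depend on outcome, because glycemic control feeds the compliance judgement and HbA1c is the primary endpoint. With no data collected specifically for a compliance analysis, the basis of each judgement would be hard to examine later. Second, a patient taken off IP but kept in the study could join the small group from which ITT imputations are drawn; a patient removed from the study cannot. Third, SAP Table 6.2 limits the ITT analysis of postprandial excursions to patients with a post-baseline observation. The visible text describes no imputation for excursions, although SAP 6.3 is partly redacted. A removed patient would therefore appear to drop out of the 1-hour and 2-hour excursion tests.

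**Working it through.** **1. Reading the sections together.** 8.1 encourages retention, 8.2 permits investigator-decided study discontinuation, and 7.6 applies that permission to noncompliance. So 7.6 agrees with 8.2 and is in tension with the purpose of 8.1. Only 7.3 expresses the stricter form, for a different event.

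**2. The plan's own figures** (Protocol 10.1: margin 0.4, SD 1.1, true difference 0, 284 completers per arm, two-sided 95% CI).

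- SE = 1.1 × √(2/284) = 0.092
- Power = Φ(0.4/0.0923 − 1.96) = Φ(2.37) = 99.1%, matching the stated figure of more than 99%
- Non-completion = 1 − 568/670 = 15.2%; 568/0.85 rounds up to 669, matching the stated 670 or so

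**3. Precision if removals come on top of the planned losses.** The rate x is an assumption. Observed n per arm = (568 − 670x)/2.

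| Extra removed | n per arm | Power at 0.4 |
|---|---|---|
| 1% | 281 | 99.1% |
| 2% | 277 | 99.0% |
| 5% | 267 | 98.8% |
| 10% | 251 | 98.3% |

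Power is not the issue.

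**4. Shift in one arm's mean.** Suppose k patients are removed from one arm and their true Week 26 value is d points worse than the imputed one. The arm mean is then off by (k/335) × d. The denominator is 335 (670/2) because the ITT ANCOVA takes all randomized patients after imputation. Both k and d are assumptions.

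- k = 10: 10/335 × 0.5 = 0.015; 10/335 × 1.0 = 0.030
- k = 20: 20/335 × 0.5 = 0.030; 20/335 × 1.0 = 0.060
- Against the SE of 0.092 on which the trial is sized: 0.015/0.092 = 0.16 up to 0.060/0.092 = 0.65

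The direction depends on the arm. Removals from the LY900014 arm make it look better than it is; removals from the insulin lispro arm do the reverse.

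**5. Effect on the noninferiority reading.** The CI half-width is 1.96 × 0.0923 = 0.181. With an observed difference of zero, the largest shift in step 4 moves the upper limit to 0.181 + 0.060 = 0.241, below both 0.4 and the alternative margin of 0.3.

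**6. Balance.** With k₁ and k₂ removals and a common d, the treatment difference shifts by (k₁ − k₂)/335 × d, which is zero when the counts match.

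**The case against.** The strongest reply is that nothing here is contradictory or uncontrolled. 8.1 encourages, 8.2 permits, and 7.6 is consistent with both. Removal is optional, needs consistent noncompliance, follows re-education, and has stopping IP only as an alternative. Some patients who are noncompliant because they miss visits would supply no Week 26 value under any wording. The planned 15.2% non-completion may already include such withdrawals, and investigators are blinded, which makes one-sided removal less likely. All of this stands, and it limits the size of the point.

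Several stronger readings are tempting, and the documents do not support them:

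- *That 7.6 contradicts a retention rule.* 8.1 contains encouragement, not a bar on study discontinuation.
- *That the patient's data are lost altogether.* Earlier data are kept, an early discontinuation visit and Visit 801 are done, and Week 26 HbA1c is imputed. Protocol 10.3.3.1.1 and SAP 6.11.4 plan a delta stress test that includes delta equal to the margin. That test probes the imputation assumption; it does not recover the value.
- *That poor glycemic control by itself triggers removal.* It is one input of three.
- *That 8.1.3 has the same defect.* The discussion there is "to determine if the patient may continue in the study", but it turns on medical appropriateness and already allows continuation with or without IP.

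What survives is narrower: a willing randomized patient can be taken out of follow-up for noncompliance alone, and the estimand gains nothing from that.

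**Conclusion.** The point holds as an avoidable weakness in the follow-up rules, not as an error in any figure or analysis. Sections 7.6, 8.1 and 8.2 leave open whether noncompliance alone can end follow-up after randomization. Where it does, the missing Week 26 values may be informative and the imputation reference group loses a potential member. Whether this would tip the analysis into the return-to-baseline fallback cannot be judged from the documents.

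The assumed shift of 0.015 to 0.060 HbA1c points in one arm is small against the 0.4 margin. It matters somewhat more for the HbA1c superiority test, which has no margin to absorb it. The range rests on assumed counts of 10 to 20 removals, all in one arm, and an assumed gap of 0.5 to 1.0 points between true and imputed values. The documents give neither, and balanced removals would largely cancel. The case for acting is that the remedy is cheap, not that the expected bias is large.

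**What to change.** For randomized patients, reword 7.6 so that the existing option to discontinue IP for noncompliance stands, but the patient should remain in the study for scheduled visits unless consent is withdrawn. This is the form 7.3 already uses. Limit discontinuation from the study for noncompliance to the lead-in period. Align 8.2 so that noncompliance alone is not a reason to end follow-up after randomization; otherwise the same route stays open through its general investigator-decision entry. Leave unchanged the rules on when IP is stopped, the patient's right to withdraw, and the medical judgement in 8.1.3.

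The cost is a few sentences in a protocol amendment, plus modest site effort to follow poorly adherent patients at visits already in the schedule. No change to the sample size or the analysis model is needed.

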7.7. Concomitant Therapy

Guidance on restrictions for concomitant therapies is provided in [Table ITRN.8](#).

Table ITRN.8. Concomitant Medications

Drug Class	Acute Use	Chronic Use	Safety Follow-up and Insulin Lispro Antibody Follow-Up Periods	Conditions for Use
Sulfonylurea, meglitinide, DPP-4 inhibitor, alpha-glucosidase inhibitor	No	No	Yes	
Thiazolidinedione, glucagon like peptide-1 receptor agonist	No	No	No	
NPH insulin, insulin glargine U-300, insulin detemir	No	No	Yes	
Premixed insulin or premixed insulin analog	No	No	Yes	
Insulin human inhalation powder (Afrezza®)	No	No	No	
Weight loss drugs (for example, prescription drugs: liraglutide, lorcaserin, orlistat, phentermine, phentermine/topiramate, naltrexone/bupropion; or over-the-counter weight loss medications)	No	No	Yes	
Systemic glucocorticosteroid (including IV, intramuscular, SC, or oral but excluding topical, inhaled, intraocular, intra-articular, or intranasal preparations)	Yes	No	No	During the lead-in period, allow 1-time use for ≤7 consecutive days. During all other study periods, allow 1-time use ≤14 consecutive days.

Abbreviations: IV = intravenous; NPH = neutral protamine Hagedorn; SC = subcutaneous.

7.7.1. Management of Oral Antihyperglycemic Medications

During the study lead-in and treatment periods, patients may continue the use of up to 2 of the following OAMs: metformin, SGLT2 inhibitor. Please also refer to Section 6.2, Exclusion Criterion [31] for criteria regarding thiazolidinediones, GLP-1 receptor agonists, and pramlintide. Other prestudy OAMs including sulfonylurea, meglitinide, DPP-4 inhibitor, and alpha-glucosidase inhibitor agents will be discontinued at the beginning of the lead-in period (Visit 2).

OAM dosing is to remain stable during study lead-in and treatment, except with the development of contraindications or for safety reasons. During study lead-in and treatment, all glycemic management is to be conducted by adjustment of basal and prandial insulin doses. In emergency situations, it may be necessary for patients to change their dose of OAM and/or be treated with a nonstudy insulin. This will be allowed for up to 14 consecutive days (Section 8.1.2).

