8.1.2. Temporary Discontinuation from Study Treatment

During the study, patients who temporarily discontinue the IP may be able to resume IP based on the following scenario:

Patient has not taken IP for 14 consecutive days or less:

- If the treatment regimen restarts within 14 days of when the patient initially stopped taking IP, patient may continue in the study and begin treatment again with IP. During this time, nonstudy insulins may have been used. If the patient decides to continue in the study, no early termination procedures will be completed. Patients will continue study visits through the safety follow-up.

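### Short emergency use of certain nonstudy insulins is allowed with IP resumed in Protocol 7.7.1 and 8.1.2, but is a mandatory reason for permanent IP discontinuation under 8.1.1 and Table ITRN.8

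*Protocol*

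**What the plan says.** Four places in the current protocol text bear on this.

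- **Section 7.7.1** (oral medications) closes with an emergency allowance. A patient may "be treated with a nonstudy insulin. This will be allowed for up to 14 consecutive days", with a pointer to 8.1.2. No type of insulin is excluded.
- **Section 8.1.2** covers an IP gap of 14 consecutive days or less. It says "During this time, nonstudy insulins may have been used" and lets the patient go back on IP.
- **Table ITRN.8** (Section 7.7) has a row for "NPH insulin, insulin glargine U-300, insulin detemir", a row for "Premixed insulin or premixed insulin analog" and a row for inhaled insulin. Each is marked No for acute and No for chronic use, and the conditions column is blank.
- **Section 8.1.1** opens its list with "Patients will be discontinued from the IP in the following circumstances". One item is "Use of prohibited concomitant medication", which refers to Table ITRN.8. Another covers a patient who needs, for whatever reason, a different regimen or agent known to work in the study indication. A third is more than 14 consecutive days without IP.

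Neither 8.1.1 nor the table mentions 7.7.1 or 8.1.2.

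On the analysis side, the efficacy estimand takes data up to permanent IP discontinuation (Protocol 10.3.3.1, SAP 6.11.1). SAP 6.1 dates on-IP status from the last IP dose: that date for the meal test, 14 days later for other office-visit data, and 1 day later for diary-type records.

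**The concern.** For the insulins listed in Table ITRN.8, the protocol gives two answers to one question: may the patient return to IP after a few days of emergency treatment? One pair of passages says yes. The other pair says IP must stop permanently.

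The answer decides the last IP dose date, and several analysis sets and data cut-offs hang on that date or on the fact of permanent discontinuation:

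- which HbA1c, meal-test and hypoglycemia data count as on IP;
- who is a Completer and who can be Per Protocol;
- who belongs to the ITT reference group, made up of same-arm patients who stopped IP and finished the study without missing data.

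Two important-deviation checks in SAP Table 6.3 may also be affected. *Excluded Conmeds* is judged against Table ITRN.8, and *Violation of Discontinuation Criteria* against Protocol Section 8. A site that relied in good faith on 7.7.1 could be flagged under both.

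**Working it through.** This is a textual contradiction, so the main check is to apply each pair of passages to the same patient.

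**1. Which insulins conflict.**
- NPH, glargine U-300, detemir, premixed and inhaled insulin are in Table ITRN.8, so 8.1.1 applies directly. The conflict with 7.7.1 and 8.1.2 is literal.
- Aspart, glulisine and regular insulin, named in Inclusion Criterion 3, are not in the table. For these the only tension comes from the 8.1.1 item on needing a different effective regimen or agent.
- The item on more than 14 days without IP agrees with 8.1.2, so there is no conflict there.

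**2. One hypothetical patient.** Suppose IP is interrupted at Week 14, NPH is given for three days, and the patient stays in the study to Week 26. The HbA1c visits in the efficacy model are 11, 13, 15 and 18, that is Weeks 4, 8, 12 and 26.
- *Following 7.7.1 and 8.1.2:* IP resumes and the last dose falls at the end of treatment. HbA1c at all four visits and the Week 26 meal test are on IP. The patient can be a Completer and is not in the ITT reference group.
- *Following Table ITRN.8 and 8.1.1:* the last dose is at Week 14, so the office-visit cut-off is Week 14 + 2 = Week 16. HbA1c at Weeks 4, 8 and 12 stays, but Week 26 drops out of the efficacy estimand, as does the Week 26 meal test. The patient is neither a Completer nor Per Protocol, and joins the ITT reference group if no data are missing.
- *Under either route:* an observed Week 26 HbA1c is used in the ITT analysis, which takes all data regardless of IP use.

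**3. Power.** Protocol 10.1 gives a margin of 0.4%, SD 1.1%, no true difference, 284 completers per group and a two-sided 95% interval.
- Standard error = 1.1 × √(2/284) = 0.0923.
- Power = Φ(0.4/0.0923 − 1.96) = Φ(2.37) = 0.9912. The noncentral t with 566 degrees of freedom gives 0.9910. The stated figure of more than 99% is reproduced.
- If 1%, 2%, 5% or 10% of the 568 completers lost their on-IP Week 26 value (assumed shares), power would be 99.1%, 99.0%, 98.8% or 98.4%.

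**4. How many patients.** The documents give no frequency. If 1% to 3% of the 670 randomized patients had any emergency nonstudy-insulin episode (an assumption), that is 0.01 × 670 ≈ 7 to 0.03 × 670 ≈ 20 patients. A patient changes status only if the insulin was a listed one and the site's choice of passage differs, so 7 to 20 is an upper bound under that assumption.

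**5. The ITT reference group.** Its size cannot be derived. The Synopsis describes the 568 as finishing treatment, which leaves 670 − 568 = 102 who do not (51 per arm if balanced). The reference group would be those among them who stay to the end. Section 10.1 describes the 568 as completing the study, and on that reading the 102 say nothing about this group.

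**The case against.** The best case for the plan is that the passages can be read together. Section 7.7 presents Table ITRN.8 as guidance on restrictions. Subsection 7.7.1 sits directly beneath it, deals with one special situation and cites 8.1.2. The 14-day limit there matches the off-IP limit in 8.1.1. On that reading the emergency allowance is a specific exception to a general table, and only a cross-reference is missing.

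This is plausible, but no passage gives 7.7.1 priority. The table also writes out a short-use exception where one is intended: the glucocorticosteroid row says "During all other study periods, allow 1-time use ≤14 consecutive days". The insulin rows carry nothing of the kind, although the table has a column for acute use. A site reading the table and 8.1.1 literally would stop IP.

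Other parts of the defence stand and limit the point:

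- IP is a prandial insulin, and the usual prandial substitutes are not in the table. A reader might infer that every nonstudy insulin is both allowed and forbidden, but the direct conflict covers only the listed products.
- A reader might infer that the efficacy estimand is itself undefined. It is not: once a site has acted, SAP 6.1 classifies the data by a recorded date.
- A reader might infer that sites will treat identical patients differently. The text permits this, but nothing in the documents shows that it will happen. Site staff are blinded, so there is no reason to expect handling to differ by arm.
- The two deviation rows in SAP Table 6.3 are partly redacted, so how a short emergency episode would be flagged cannot be fully seen.
- The SAP has a return-to-baseline fallback if the reference group is too small for the imputation. That protects the analysis from failing, but it does not settle who belongs to the group.

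**Conclusion.** The contradiction is real and is in current text. For NPH, glargine U-300, detemir, premixed and inhaled insulin, the protocol both allows a short emergency course with return to IP and requires permanent discontinuation. For other nonstudy insulins the tension is weaker and rests on a single item in 8.1.1.

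The consequence is limited to which individual patients' data count as on IP, their Completer and Per Protocol status, their membership of the ITT reference group and possibly their deviation flags. The estimand definitions and the observed ITT data are untouched.

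The effect on power is negligible. The documents do not support a claim that the noninferiority conclusion is at risk, or any particular number of affected patients. The reference group is where a few reclassified patients could matter most, because it supplies the imputation model and may be small, but its size is not given. Label: wrong as written (internal contradiction), minor in size.

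**What to change.** Reconcile Protocol 7.7.1, 8.1.1, 8.1.2 and Table ITRN.8 so that one stated rule governs short emergency use of nonstudy insulin. The rule should say which insulins it covers, and each of the four places should refer to the others. It should also say how the 8.1.1 item on a different effective regimen or agent applies to a short emergency course. Which clinical rule is adopted is the sponsor's decision.

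Then align the *Excluded Conmeds* and *Violation of Discontinuation Criteria* checks in SAP Table 6.3 with that rule, so that a site following it is not recorded as deviating.

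The cost is a protocol clarification and a matching edit to the deviation checks. No analysis model, sample size or data collection changes.
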